13.2.1 Deviations From Non-Informative Censoring

For the key secondary endpoint, censoring can only occur among those subjects who complete the 26 week double-blind period or who discontinue due to the study being terminated by the sponsor. This censoring is non-informative and therefore sensitivity analyses to address informative censoring are not needed.

13.2.2 Sensitivity Analysis

Sensitivity analysis for the key secondary efficacy endpoint will be performed on the Per-protocol Analysis Set. The results will be presented in a summary table similar to that described for the key secondary efficacy analysis.

13.3 Exploratory Efficacy Analysis

13.3.1 Analysis for the Double-blind Period

Exploratory efficacy variables SAPS-H+D, SAPS Hallucinations domain, SAPS Delusions domain, CGI-S, ZBI, KSS, EQ-5D VAS, and EQ-5D-5L descriptive system evaluated in the double-blind period will be analyzed for the ITT Analysis Set. For each exploratory efficacy variable other than the EQ-5D-5L descriptive system, observed and change from double-blind Baseline values at each analysis visit will be summarized using descriptive statistics by treatment group (placebo and pimavanserin). In addition, the descriptive summaries will be provided by pimavanserin dose level (20 and 34 mg) for the double-blind pimavanserin group.

For each exploratory efficacy variable other than the EQ-5D-5L descriptive system, treatment comparisons will be made between the placebo group and the pimavanserin group (20 mg and 34 mg combined) using a MMRM and an ANCOVA. No adjustment for multiple comparisons will be made among the exploratory efficacy variables. At each post-baseline analysis visit, LS means and standard errors (SE), the corresponding 95% confidence interval and p-value will be presented. In addition, plots of LS mean \pm SE versus analysis visit will be provided.

13.3.1.1 Mixed Model Repeated Measures

For each exploratory efficacy variable other than the EQ-5D-5L descriptive system, the change from baseline will be analyzed using mixed model repeated measures (MMRM) method with missing data assumed to be missing at random. The dependent variable will be the change from double-blind Baseline. Assessments more than 14 days after last dose of study drug will be excluded from the analysis. The independent variables in the model will include treatment group (placebo or pimavanserin), designated dementia subtype, region, analysis visit, treatment group by analysis visit interaction, double-blind Baseline score, and double-blind Baseline score by analysis visit interaction. An unstructured covariance matrix will be used and the Kenward-Roger approximation will be used to adjust the denominator degrees of freedom. Observed cases will be analyzed in the model and least squares (LS) adjusted means will be estimated using observed margins.

In the event that the model fails to converge using the unstructured covariance matrix, then the following covariance structures will be modeled in the following order:

- Heterogeneous Toeplitz;
- Heterogeneous compound symmetry;
- Heterogeneous autoregressive(1);
- Toeplitz;
- Compound symmetry
- Autoregressive(1);
- Variance components.

The first covariance structure that allows for convergence will be selected for the final model.

13.3.1.2 ANCOVA

For each exploratory efficacy variable other than the EQ-5D-5L descriptive system, the change from baseline will be analyzed using an analysis of covariance (ANCOVA) at each post-baseline analysis visit and using the last observation carried forward (LOCF) method of imputation for missing data. The LOCF method will carry forward the double-blind Baseline value if necessary; assessments more than 14 days after last dose of study drug will not be carried forward. The dependent variable will be the change from double-blind Baseline. The independent variables in the model will include treatment group (placebo or pimavanserin), designated dementia subtype, region, and double-blind Baseline score. Least squares (LS) adjusted means will be estimated using observed margins.

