3.3 Open-label Period (12 Weeks)

During the open-label period, eligible subjects will begin receiving pimavanserin 34 mg once daily (QD) beginning at Week 0 (open-label Baseline). Subsequent clinic visits will occur at Weeks 2, 4, 8, and 12. Dose adjustments are permitted at scheduled or unscheduled visits until Week 4. After Week 4, the subject's dose will remain fixed at either 34 mg or 20 mg once daily.

To enter the double-blind period, eligible subjects must meet the following response criteria at Weeks 8 and 12:

- Subject experiences a $\geq 30\%$ reduction (improvement) from Week 0 (open-label Baseline) on the SAPS-H+D Total Score AND
- Subject has a CGI-I score of 1 (very much improved) or 2 (much improved), relative to Week 0 (open-label Baseline)

A subject who does not meet response criteria at Weeks 8 and 12 will be withdrawn from study drug and enter the safety follow-up period of the study.

Pharmacokinetic samples will be collected at Weeks 0, 8, and 12. Pharmacokinetic samples will also be collected, if possible, at any ET visit or the visit immediately following any SAE or following an AE leading to discontinuation.

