5.2.2 Double-blind Baseline

Double-Blind Baseline is defined as the last non-missing assessment, including those from repeated and unscheduled measurements, on or before the date of first dose of double-blind study drug.

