5.2.7 Clinical Global Impressions – Improvement Scale

The Clinical Global Impressions – Improvement (CGI-I) scale is assessed at Weeks 2, 4, 8, and 12 during the open-label period, and at Weeks 13, 14, 16, 18, 22, 26, 30, 34, and 38 during the double-blind period.

The CGI-I scale is a clinician-rated, 7-point scale that is designed to rate the improvement in the subject's hallucinations and delusions at the time of assessment, relative to the symptoms at Baseline (relative to open-label Baseline for response criteria and relative to double-blind Baseline for relapse criteria). The possible scores are 1=very much improved, 2=much improved, 3=minimally improved, 4=no change, 5=minimally worse, 6=much worse, 7=very much worse.

Missing CGI-I scores will not be imputed.

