12.1.3 Exploratory Study Endpoints

Change from double-blind Baseline on the following:

- Scale for the Assessment of Positive Symptoms-Hallucinations+Delusions (SAPS-H+D) score
- SAPS Hallucinations domain score
- SAPS Delusions domain score
- Clinical Global Impression-Severity (CGI-S)-dementia-related psychosis
- Zarit Burden Interview (ZBI) score
- Karolinska Sleepiness Scale (KSS) score
- EQ-5D VAS score and EQ-5D-5L descriptive system
- Clinical Global Impression-Improvement (CGI-I)-dementia-related psychosis

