13.3.10 CGI-I Dementia-Related Psychosis

For the double-blind period, observed CGI-I scores will be summarized using descriptive statistics at double-blind Weeks 1, 2, 4, 6, 10, 14, 18, 22, and 26. The CGI-I score will be analyzed using the MMRM and ANCOVA models as described in [Sections 13.3.1.1, 13.3.1.2, and 13.3.1.3](#). For both the MMRM and ANCOVA models, the covariate double-blind Baseline score is the double-blind Baseline CGI-S score.

For the open-label period, observed CGI-I scores will be summarized using descriptive statistics at open-label Weeks 2, 4, 8, and 12.

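### For CGI-I, the LOCF ANCOVA as written carries forward a Week 12 rating made against a different reference point, entering affected subjects 2–3 points too favourably

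*SAP*

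**What the plan says.** SAP 12.1.3 includes CGI-I among the exploratory endpoints. SAP 13.3.10 states for the double-blind period: "The CGI-I score will be analyzed using the MMRM and ANCOVA models as described in" Sections 13.3.1.1 to 13.3.1.3. The one adaptation made for CGI-I concerns the covariate: "For both the MMRM and ANCOVA models, the covariate double-blind Baseline score is the double-blind Baseline CGI-S score".

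The scope of SAP 13.3.1.2 is broad: "For each exploratory efficacy variable other than the EQ-5D-5L descriptive system, the change from baseline will be analyzed using an analysis of covariance (ANCOVA"), with missing data filled by LOCF. Its carry-forward rule is "The LOCF method will carry forward the double-blind Baseline value if necessary". Ratings taken more than 14 days after the last dose may not be carried. CGI-I is not excepted.

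SAP 5.2.2 fixes what the Baseline value is: "Double-Blind Baseline is defined as the last non-missing assessment, including those from repeated and unscheduled measurements", up to and including the day of the first double-blind dose.

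SAP 5.2.7 gives CGI-I two reference points: "relative to open-label Baseline for response criteria and relative to double-blind Baseline for relapse criteria". The footnotes to the schedules agree. Table 1, note e, ties ratings through Week 12 to Visit 2; Table 2, note b, ties ratings from Week 13 to Visit 6 (Week 12). On the scale itself, 1 is very much improved, 2 is much improved and 4 is no change.

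Protocol 3.3 makes a favourable rating at Weeks 8 and 12 a condition of randomization: "Subject has a CGI-I score of 1 (very much improved) or 2 (much improved), relative to Week 0 (open-label Baseline").

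**The concern.** Carrying a baseline value forward is meant to represent a subject who has not changed. For SAPS-H+D, CGI-S, ZBI, KSS and EQ-5D VAS it does so, because baseline minus baseline is zero. CGI-I is already a rating of change, and its reference point moves at randomization. A Week 12 rating of 1 or 2 describes the response to open-label treatment. Placed in a double-blind visit, the same number reads as further improvement since randomization.

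The rule thus enters a value from the wrong scale, always in the favourable direction, for subjects about whom nothing is known after randomization. SAP 13.3.1.3 commits to LS mean differences, p-values and effect sizes from this model at every visit, so the error would pass into reported results if the text is programmed as it stands.

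**Working it through.** The documents state no figure on this point, so there is none to reproduce. The check traces the rule and then sizes it.

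**Trace**

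1. SAP 13.3.10 sends the CGI-I score to 13.3.1.2.
2. SAP 13.3.1.2 carries the double-blind Baseline value forward when no later eligible value exists.
3. Under SAP 5.2.2, the double-blind Baseline value of CGI-I is the Week 12 rating.
4. That rating is made against Visit 2 (SAP Table 1, note e) and is 1 or 2 for a subject who meets the response criteria (Protocol 3.3).
5. Double-blind ratings are made against Week 12 (SAP Table 2, note b), where no change is 4 (SAP 5.2.7).

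**Who is affected**

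Any subject with no eligible double-blind rating by a given visit:

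- one with no double-blind rating at all, at every visit;
- one who misses Week 13 but is rated later, at DB Week 1;
- one whose only later ratings fall more than 14 days after the last dose, at every visit.

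**Error per affected value**

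Error = carried value − 4.

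- Carried 2: 2 − 4 = −2.
- Carried 1: 1 − 4 = −3.

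**How many (assumption)**

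The documents give no count. SAP 3.4 assumes 25% dropout over 26 weeks (182 days). If that rate is constant, the share lost within the first 7 days, before the Week 13 target date, is

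1 − 0.75^(7/182) = 1.1%, and 0.011 × 89 ≈ 1 subject per arm.

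This tends to overstate the subjects with no rating at all, because a discontinuing subject should have an early-termination visit (Protocol 4.4). That visit includes CGI-I (SAP Table 2) and is eligible for by-visit analysis (SAP 5.3.3). It does not count subjects who stay in the study but miss Week 13.

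**Size with 89 per arm (SAP 3.4)**

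Arm-mean shift = error × k/89, where k is the number affected in the arm. Shift in the treatment difference = error × (k_pim − k_pbo)/89. The values of k are illustrative.

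| Affected | Shift if all carried values are 2 | Shift if all carried values are 1 |
|---|---|---|
| 1 in an arm: arm mean | −2/89 = −0.022 | −3/89 = −0.034 |
| 2 in an arm: arm mean | −4/89 = −0.045 | −6/89 = −0.067 |
| 2 in each arm: difference | 0 | 0 |
| 4 versus 1: difference (absolute) | 6/89 = 0.067 | 9/89 = 0.101 |

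The difference moves in favour of the arm with more affected subjects.

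**After the change**

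If only double-blind ratings are carried forward, every carried value has the Week 12 reference and the error from mixing reference points is 0.

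**The case against.** The best counter-argument is that the SAP never calls the Week 12 CGI-I a double-blind Baseline value. Section 13.3.10 summarizes CGI-I only at double-blind Weeks 1 to 26, with no Baseline entry. The Baseline covariate is replaced by CGI-S. CGI-I is also missing from the list of variables that opens 13.3.1. On that view CGI-I has no Baseline to carry and the rule is simply undefined for these subjects. This has some force as a guess at intent. But 5.2.2 defines Baseline without exception, and 13.3.10 invokes 13.3.1.2 by number without altering the carry-forward rule. A programmer following the text arrives at Week 12, and an undefined rule would need the same sentence to settle it.

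A second argument is that SAP 5.2.7 says missing CGI-I scores are not imputed. SAP 5.2.6 and 5.2.9 say the same of CGI-S and KSS, and both of those go to LOCF, so the sentence does not exempt CGI-I.

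A reader might infer more from SAP 12.1.3, which lists CGI-I under change from double-blind Baseline: that the Week 12 rating is to be subtracted from every later one, which would corrupt the MMRM as well. The analysis sections do not support this. Protocol 9.5.3 gives CGI-I a model sentence of its own, apart from the change endpoints. SAP 12.2 keeps the same separation. SAP 13.3.10 analyses the score and omits the change-from-Baseline summary that the other scales have. The heading in 12.1.3 is loose wording.

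A reader might also infer a bias toward one named arm, or a large one. The documents do not say which arm would have more affected subjects, and they give no basis for a share much above 1%.

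What stands without dispute is that the consequence is limited. CGI-I is exploratory, and Protocol 9.5.3 makes LOCF an addition to the MMRM.

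**Conclusion.** The point holds as a defect in a stated rule with a small effect. Followed literally, the LOCF ANCOVA for CGI-I gives a subject with no eligible double-blind rating a value 2 to 3 points more favourable than no change.

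One affected subject in an arm of 89 moves that arm's mean by about 0.02 to 0.03. The tested treatment difference moves only to the extent that the arms differ in the number affected. The count of about one per arm is an assumption (constant dropout of 25% over 26 weeks, no early-termination rating), and the statement that the carried value is 1 or 2 assumes that nobody is randomized in breach of the response criteria.

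The problem is confined to the exploratory CGI-I LOCF ANCOVA. The MMRM uses observed cases and is unaffected. The primary and key secondary analyses do not use this rule.

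**What to change.** Add to SAP 13.3.10: for CGI-I, only ratings made in the double-blind period are carried forward; the Week 12 rating is never carried; a subject with no eligible double-blind rating at or before a visit is not included in the CGI-I LOCF ANCOVA at that visit.

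This is preferable to assigning 4 to such subjects. Assigning 4 would be an imputation not derived from any rating and would sit badly with SAP 5.2.7. Under the proposed rule, a subject who misses Week 13 is absent at DB Week 1 and enters at the first later visit with an eligible rating.

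The cost is one sentence, settled before unblinding, with no change to conduct or data collection. The downside is that a few ITT subjects drop out of this exploratory analysis, so its number of subjects may vary slightly across visits and should be shown.

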13.3.1.3 Treatment Comparisons

For each exploratory efficacy variable other than the EQ-5D-5L descriptive system, the treatment comparisons will be based on the difference in LS means obtained from the statistical model (MMRM or ANCOVA) at each post-baseline analysis visit for the respective exploratory efficacy variable and will be tested at a 2-sided alpha level of 0.05.

Summary statistics for the observed and change from Baseline values will be presented for all analysis visits. For the change from double-blind Baseline values at each post-baseline analysis visit, LS means and standard errors (SE), the between-group difference in LS means

with the corresponding 95% confidence interval, p-value and effect size will be presented. In addition, LS mean \pm SE over time for the change from Baseline values by treatment group will be presented in line plots.

At each post-baseline analysis visit, the effect size (Cohen's d) for the change from double-blind Baseline between the treatment groups will be calculated using the following formula:

$$Effect\ size = \frac{LS\ mean\ difference}{\sqrt{variance}}$$

where the variance at a given visit will be obtained from the covariance matrix estimated for the MMRM model or the mean squared error obtained from the ANCOVA model. The sign (+ or -) of the effect size will be chosen so that a positive value favors pimavanserin.

13.3.2 Analysis for the Open-label Period

Exploratory variables SAPS-H+D, SAPS Hallucinations domain, SAPS Delusions domain, CGI-S, ZBI, KSS, EQ-5D VAS, and EQ-5D-5L descriptive system assessed in the open-label period will be summarized for the Open-label Safety Analysis Set.

For each exploratory variable other than the EQ-5D-5L descriptive system, the observed and change from open-label Baseline values at each analysis visit will be summarized using descriptive statistics. The following summaries will be provided:

1. all subjects combined;
2. by randomization status (not randomized and randomized);
3. by final dose level (20 and 34 mg) of open-label pimavanserin.

The mean change from open-label Baseline to each analysis visit and 95% CI will be provided for the following exploratory endpoints: SAPS-H+D, SAPS Hallucinatin domain, SAPS Delusions domain, CGI-S, ZBI, KSS and EQ-5D VAS.

13.3.3 SAPS-H+D

For the double-blind period, observed SAPS-H+D total score will be summarized using descriptive statistics at double-blind Baseline, double-blind Weeks 1, 2, 4, 6, 10, 14, 18, 22, and 26. The change from double-blind Baseline values will also be summarized at the double-blind Weeks 1, 2, 4, 6, 10, 14, 18, 22, and 26. The change from double-blind Baseline

in SAPS-H+D total score will be analyzed using the MMRM and ANCOVA models as described in [Sections 13.3.1.1, 13.3.1.2, and 13.3.1.3](#).

For the open-label period, observed SAPS-H+D total score will be summarized using descriptive statistics at open-label Baseline, open-label Weeks 2, 4, 8, and 12. The change from open-label Baseline values will also be summarized at the open-label Weeks 2, 4, 8, and 12.

13.3.4 SAPS Hallucinations Domain

For the double-blind period, observed SAPS Hallucinations domain score will be summarized using descriptive statistics at the double-blind Baseline and Weeks 1, 2, 4, 6, 10, 14, 18, 22, and 26. The change from double-blind Baseline values will also be summarized at the double-blind Weeks 1, 2, 4, 6, 10, 14, 18, 22, and 26. The change from double-blind Baseline in SAPS Hallucinations domain score will be analyzed using the MMRM and ANCOVA models as described in [Sections 13.3.1.1, 13.3.1.2, and 13.3.1.3](#).

For the open-label period, observed SAPS Hallucinations domain score will be summarized using descriptive statistics at the open-label Baseline, Weeks 2, 4, 8, and 12. The change from open-label Baseline values will also be summarized at the open-label Weeks 2, 4, 8, and 12.

13.3.5 SAPS Delusions Domain

For the double-blind period, observed SAPS Delusions domain score will be summarized using descriptive statistics at the double-blind Baseline and Weeks 1, 2, 4, 6, 10, 14, 18, 22, and 26. The change from double-blind Baseline values will also be summarized at the double-blind Weeks 1, 2, 4, 6, 10, 14, 18, 22, and 26. The change from double-blind Baseline in SAPS Delusions domain score will be analyzed using the MMRM and ANCOVA models as described in [Sections 13.3.1.1, 13.3.1.2, and 13.3.1.3](#).

For the open-label period, observed SAPS Delusions domain score will be summarized using descriptive statistics at the open-label Baseline and Weeks 2, 4, 8, and 12. The change from open-label Baseline values will also be summarized at the open-label Weeks 2, 4, 8, and 12.

13.3.6 CGI-S Dementia-Related Psychosis

For the double-blind period, observed CGI-S score will be summarized using descriptive statistics at the double-blind Baseline and Weeks 1, 2, 4, 6, 10, 14, 18, 22, and 26. The change from double-blind Baseline values will also be summarized at the double-blind Weeks 1, 2, 4, 6, 10, 14, 18, 22, and 26. The change from double-blind Baseline in CGI-S score will be analyzed using the MMRM and ANCOVA models as described in [Sections 13.3.1.1](#), [13.3.1.2](#), and [13.3.1.3](#).

For the open-label period, observed CGI-S score will be summarized using descriptive statistics at the open-label Baseline and Weeks 2, 4, 8, and 12. The change from open-label Baseline values will also be summarized at the open-label Weeks 2, 4, 8, and 12.

13.3.7 Responder Analysis

For the open-label period, the number and percentage of subjects in the Open-label Safety Analysis Set that met the following response criteria ($\geq 30\%$ reduction from open-label Baseline on SAPS-H+D Total Score and CGI-I score of 1 or 2, relative to open-label Baseline) will be provided for Week 2, Week 4, Week 8, and Week 12, and at both Weeks 8 and 12.

13.3.8 ZBI Score

For the double-blind period, observed ZBI scores will be summarized using descriptive statistics at the double-blind Baseline and Weeks 6, 14, and 26. The change from double-blind Baseline values will also be summarized at the double-blind Weeks 6, 14, and 26. The change from double-blind Baseline in ZBI score will be analyzed using the MMRM and ANCOVA models as described in [Sections 13.3.1.1](#), [13.3.1.2](#), and [13.3.1.3](#).

For the open-label period, observed ZBI score will be summarized using descriptive statistics at the open-label Baseline and Week 12. The change from open-label Baseline values will also be summarized at the open-label Week 12.

13.3.9 KSS Score

For the double-blind period, observed KSS scores will be summarized using descriptive statistics at double-blind Baseline and Weeks 6, 14, and 26. The change from double-blind

Baseline values will also be summarized at the double-blind Weeks 6, 14, and 26. The change from double-blind Baseline in KSS score will be analyzed using the MMRM and ANCOVA models as described in [Sections 13.3.1.1, 13.3.1.2, and 13.3.1.3](#).

For the open-label period, observed KSS scores will be summarized using descriptive statistics at open-label Baseline and open-label Week 12. The change from open-label Baseline values will also be summarized at the open-label Week 12.

13.3.10 CGI-I Dementia-Related Psychosis

For the double-blind period, observed CGI-I scores will be summarized using descriptive statistics at double-blind Weeks 1, 2, 4, 6, 10, 14, 18, 22, and 26. The CGI-I score will be analyzed using the MMRM and ANCOVA models as described in [Sections 13.3.1.1, 13.3.1.2, and 13.3.1.3](#). For both the MMRM and ANCOVA models, the covariate double-blind Baseline score is the double-blind Baseline CGI-S score.

For the open-label period, observed CGI-I scores will be summarized using descriptive statistics at open-label Weeks 2, 4, 8, and 12.

13.3.11 EQ-5D VAS

For the double-blind period, observed EQ-5D VAS scores will be summarized using descriptive statistics at double-blind Baseline and double-blind Weeks 6, 14, and 26. The change from double-blind Baseline values will also be summarized at the double-blind Weeks 6, 14, and 26. The change from double-blind Baseline in QD-5D VAS score will be analyzed using the MMRM and ANCOVA models as described in [Sections 13.3.1.1, 13.3.1.2, and 13.3.1.3](#).

For the open-label period, observed EQ-5D VAS scores will be summarized using descriptive statistics at open-label Baseline and Week 12. The change from open-label Baseline scores will also be summarized at the open-label Week 12.

